Participants will be randomized to the *Experimental Group* and received the ICBT intervention for 8-weeks, or the *Control Group* whose participants will be monitored weekly during this 8-week period. During the first phase the experimental group will completed the intervention. Following this both groups will complete T1 (post-treatment) outcome measures. During the second phase, the control group will receive the same ICBT intervention, after which both groups will complete T2 (2 month follow-up) outcomes. This study design, therefore, provided the opportunity to evaluate the intervention effects in two independent groups at three time points as shown in Figure 1.

Study Population

Study eligibility

Inclusion criteria:

- Adults, aged 18 years and over, living in Texas in the US;
- The ability to read and type in English or Spanish;
- Access to a computer, the internet and able to email;
- Experiencing tinnitus for a minimum period of three months and
- A tinnitus severity score of 25 or greater on the Tinnitus Functional Index (TFI) indicating the need for an intervention.

Exclusion criteria:

• Indication of significant depression (≥ 15) on the Patient Health Questionnaire (PHQ-9);

- Indications of self-harm thoughts or intent, answering affirming on Question 10 of the PHQ-9 questionnaire;
- Reporting any medical or psychiatric conditions that could interfere with the treatment;
- Reporting pulsatile, objective or unilateral tinnitus, which has not been investigated medically or tinnitus still under medical investigation; and
- Undergoing any tinnitus therapy concurrent with participation in this study.

Eligibility will be determined by a two-stage process as follows:

- An online screening questionnaire, which includes demographic information, health and mental health-related questions, and standardized outcome measures as shown in Table 1.
- A telephone interview during which the researcher will recheck eligibility, and provided the opportunity for potential participants to ask any questions related to the study. The study procedures will be explained, and motivational interviewing will be done to encourage participants to commit and engage in the intervention.

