Participants meeting the inclusion criteria will be randomly assigned in the ratio of 1:1 and enrolled to either the experimental or control group using a computer-generated randomization scheduled by an independent research assistant in blocks of varying sizes after participants are pre-stratified for language (English and Spanish).

Patient Public Partnership (PPI)

A PPI will be established to include two individuals with tinnitus who had piloted the ICBT intervention, two audiologists, two researchers. Meetings will be held via video conferencing. The aim of the PPI will be to guide the study processes and input into the research strategy to boost recruitment and other elements of the study to ensure high compliance and engagement.

Intervention

The ICBT intervention content will be based on a CBT self-help program originally developed in Swedish (Andersson & Kaldo, 2004) and later adapted and translated in English (Abbott, et al., 2009). The intervention will be subsequently transformed into an 8-week interactive e-learning version suitable for a UK population (Beukes, et al., 2016) and then adapted linguistically and culturally to ensure suitability for a US population (Beukes, et al., 2020). These adaptions prioritized accessibility of the intervention, such as lowering the readability to below the recommended 6th-grade level, as more than half the US adult population have low literacy skills (Statistics, 2003). The intervention will be augmented by a module on mindfulness and more videos. The ICBT platform in the US application consisted of 22 modules with worksheets and quizzes (see Beukes et al., 2020; Beukes et al., 2021a for more details).

The intervention platform will be transferred from Sweden and housed in the US (Lamar University) to comply with the needed US data protection regulations. Prior to this feasibility trial, acceptability and functionality of this intervention for a US population will be first ensured (Manchaiah et al., 2020). Further details about the features, functionalities, and intervention components are presented in Manchaiah et al. (2020).

Both groups will received the same intervention, only the timings regarding receiving the intervention will vary. The control group will receive the experimental intervention 8 weeks after the experimental group commenced the program.

Audiology Guidance

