Online questionnaires will be used throughout the study. All the measures will be completed at baseline, T1 (post-intervention for experimental group), T2 (post-intervention for the control group and at two-month follow-up for the experimental group). To have a measure of the control group 2 months post intervention, participants completed further outcome measures at T3. For data analysis purposes the T3 results for the control group and those at T2 for the experimental group will be compared in order to assess the invention effect at same experimental time point for both groups (i.e., 2 months post intervention). To maximize retention, 3 electronic reminders will be sent to participants who had not completed questionnaires, on the 3 consecutive days after the release of the questionnaire. A further reminder will be sent out via email and text message. If questionnaires will be still not completed participants will be telephoned to encourage questionnaire completion. Participants will be also phoned after completing the intervention to discuss the progress they had made and share their questionnaire results.

Statistical Analysis Plan

Statistical analyses will be performed using the Statistical Package for Social Sciences (SPSS) version 26.0. All statistical tests will be 2- tailed with an alpha set to .05. To account for missing data from participants not completing the post-intervention or follow-up intervention analysis an imputation analysis will be undertaken. Missing data will be handled through multiple imputation using the *Markov Chain Monte Carlo* approach (Jakobsen et al.,

2017). For comparison, a complete case analysis will be also performed by analyzing only the completed questionnaire data without imputing missing data. As there will be substantial differences, statistical analysis using the imputed data are reported in the results section.

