The primary study outcome will be a change in TFI score between the groups at postintervention (T1). A difference in scores between T1–T2 for the experimental group will be used to assess the stability of intervention effects. According to recommendations for statistical analysis of internet interventions effect sizes, linear mixed effects models, and the reliable change index will be used to assess the primary and secondary outcomes (Hesser, 2015). Changes from baseline to post-intervention will be compared within and between groups using the pre-post-test effect size (Cohen's *d*) for all primary and secondary outcomes using the observed data. Effect sizes of d = 0.20 represent small effect sizes; those of d =0.50, medium effect sizes; and those equal or greater than d = 0.80, large effect sizes (Cohen, 1992).

A Linear Mixed Model (LMM), which provides unbiased results in the presence of missing data (using all available data), will be applied to analyze the intervention effect over time for each outcome measure. An unstructured-repeated effects and identify-random effects covariance structure provided the best model fit based on the Akaike's Information Criterion (AIC). Time will be treated as a repeated and fixed effect. Restricted maximum likelihood estimation will be applied. The Type III F test sums of squares from the LMM will be calculated. As a sensitivity analysis, baseline tinnitus severity will be initially added as a covariate, but as it had no significant effect on the results it will be removed from the model.

Another model will be run to test the differences during the course of the 8 weeks intervention for the weekly outcome measures. Post hoc time comparison will be carried out in the case of significant group differences to assess at which time points these differences occurred.

In addition to statistical significant, clinical significance will also reported. A 13 point difference is recommended by the original developers of the TFI (Meikle et al, 2012) to indicate a meaningful change in scores. To handle study variability, the reliable change index (RCI) (Jacobson & Truax, 1991) is recommended as a means of calculating clinical significance for the TFI as the primary outcome. This will be calculated using the mean pretest-posttest score difference, the pretreatment standard deviation (17.49), and a test-retest reliability coefficient of 0.78, and as reported in the validation study

Sample Characteristics

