Descriptive statistics including gender, age, ethnicity, race, tinnitus duration, hearing aid use, and professionals consulted, ease of computer use, veteran status, education and employment status will be used to describe the sample. The means and standard deviations will be reported for each outcome measure at each time point. Descriptive statistics will be also used to describe the sample and intervention engagement including the number of logins and modules read. A Chi square test of independence will be used to identify group differences regarding engagement and compliance rates.

Dimension	Outcome Measures	Internal consistency	Range of scores	Levels of significance	Timeframe : T0 (baseline)	Timeframe: T1	Timeframe: T2	Timefra me: T3
Explanation						Post- intervention for the experimental group; post weekly monitoring for the control group	2 month follow-up for experiment al group, postinterve ntion for the control group	2 month follow-up for the control group
Tinnitus distress	Tinnitus Functional Index (TFI; Meikle et al, 2012)	.97	0-100 A reduction of scores indicates improvement	>25= mild (no need for intervention) 26-50= significant (possible need for intervention) 50+ =severe (need for a more intense	Both groups x	Both groups	Both groups	Control group only x
Generalized Anxiety	Generalized Anxiety Disorder (GAD-7, Spitzer, Kroenke, Williams, et al., 2006)	.89	0-21 A reduction of scores indicates improvement	intervention) 0-4= minimal anxiety 5-9= mild anxiety 10-14= moderate anxiety 5-21= severe anxiety	X	x	x	x

Table 1. Study outcome measures used pre-intervention, post-intervention and at 2-months follow-up

Depression	Patient Health Questionnai re (PHQ-9; Spitzer, Kroenke	.83	0-27 A reduction of scores indicates improvement	5-9=mild depression 10-14=moderate 15-19=moderately severe 20-18= severe depression	x	X	X	x
	Williams, 1999)							
Insomnia	Insomnia Severity Index (ISI; Bastien, Vallières, & Morin, 2001)	.74	0-28 A reduction of scores indicates improvement	0-7 = Not clinically signi 8-14 = Subthreshold inso 15-21 = Clinical insomnia (moderate severity) 22-28 = Clinical insomnia (severe degree)	X	Х	X	X
Tinnitus Cognitions	Tinnitus Cognitions Questionnai re (TCQ; Wilson & Henry, 1998)	.91	0-104 A reduction of scores indicates improvement	Higher scores indicate a greater tendency to engage in negative cognitions in response to tinnitus	X	Х	X	X

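### Comparing the experimental arm at T2 with the control arm at T3 cannot measure the ICBT effect, because both arms have been treated by then; the planned stability analysis also leaves out the control T2–T3 change

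*Combined protocol and SAP*

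**What the plan says.** The trial has a delayed-intervention design. Under the first Randomization heading, after Study Design, the experimental arm is treated for eight weeks while controls are monitored weekly, and both arms are then measured at T1. "During the second phase, the control group will receive the same ICBT intervention", and both arms are measured again at T2. The Intervention section confirms that the arms differ only in timing: "Both groups will received the same intervention, only the timings regarding receiving the intervention will vary".

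Questionnaire Administration adds a further visit for controls: "To have a measure of the control group 2 months post intervention, participants completed further outcome measures at T3". Table 1 labels T3 as "2 month follow-up for the control group". The same section then states that the "T3 results for the control group and those at T2 for the experimental group will be compared in order to assess the invention effect", and explains that this places both arms two months after their own treatment.

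The Statistical Analysis Plan puts the primary contrast at T1. For Objective 3 (stability two months after treatment, with no arm named under Study Objectives) it says that the T1–T2 difference "for the experimental group will be used to assess the stability of intervention effects". It names no control T2–T3 contrast.

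**The concern.** A between-arm comparison estimates a treatment effect only if one arm is treated and the other is not. In this trial that holds at T1 only. By experimental T2 and control T3 everyone has been offered the same programme, so the difference reflects delay, calendar time or differential dropout.

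As worded, a T2/T3 difference near zero would be read as a statement about the intervention effect. It could be taken to mean that the effect has gone, or that it has been confirmed. It supports neither reading, because zero is expected whether ICBT works well or not at all (given equal effects, no trend and no differential dropout).

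The second issue is smaller. The control T2–T3 change covers the same two-month post-treatment window as the experimental T1–T2 change and is collected. Leaving it out of the stability analysis gives a wider interval than the data allow.

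**Working it through.** **Inputs from the plan.** There are 58 evaluable per arm with a 20% missing-data allowance (Sample Size, Power and Attrition). The recruitment figure reproduces: 58/0.8 = 72.5, rounded up to 73 per arm, 146 in total. Pretreatment TFI SD is 17.49 and test-retest reliability 0.78 (Statistical Analysis Plan). Meaningful change is 13 points (Primary Outcome Measure). Tests are two-sided at 0.05.

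**Assumptions.** The SD is the same at every visit, with 22 as an assumed upper value. The post-to-follow-up correlation r is 0.5 (assumed) or 0.78 (the reliability used as a proxy). Two months is eight weeks, so T1, T2 and T3 fall at about weeks 8, 16 and 24 from the experimental arm's start. Control numbers of 30 and 40 at T3 are illustrative; 46 is 58 less a further 20%. Scores are unadjusted.

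**Expected values.** Let μ be the common baseline mean, D the reduction due to ICBT and b the background trend per eight weeks.

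- T1: (μ − D + b) − (μ + b) = −D.
- Experimental T2 minus control T3: (μ − D + 2b) − (μ − D + 3b) = −b.

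D drops out of the second line. If the effects differ between arms, D_E and D_C, the result is −(D_E − D_C) − b. The comparison therefore measures immediate against delayed delivery, mixed with elapsed time.

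**Simulation** (4,000 runs per row, 58 per arm, SD 17.49, within-person correlation 0.6, b = 0):

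| True D | Mean T1 difference | Mean T2/T3 difference | T2/T3 tests with p<0.05 |
|---|---|---|---|
| 0 | 0.03 | 0.01 | 5.0% |
| 6.5 | −6.58 | −0.08 | 5.8% |
| 13 | −12.98 | 0.02 | 4.8% |
| 20 | −19.91 | 0.02 | 5.2% |

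A second simulation used correlation 0.78 and an assumed natural improvement of 3 points per eight weeks (b = −3). The T2/T3 difference was about +3 and was significant in 14–15% of runs, for D of 0, 13 and 26 alike.

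**Power at T1 for D = 13.** The standard error is 17.49 × √(2/58) = 3.25, so the noncentrality is 13/3.25 = 4.0 on 114 df. Power is 0.978 (0.884 at SD 22).

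**Precision of the T2/T3 difference.** The 95% half-width is t × SD × √(1/58 + 1/n₂):

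| Controls at T3 (n₂) | SD 17.49 | SD 22 |
|---|---|---|
| 58 | 6.43 | 8.09 |
| 46 | 6.85 | 8.62 |
| 40 | 7.14 | 8.98 |
| 30 | 7.82 | 9.84 |

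**Precision of the stability estimate.** The SD of change is 17.49 × √(2(1 − r)), which is 17.49 at r = 0.5 and 11.60 at r = 0.78. The half-width is t × SD of change / √n, with n = 58 for one arm and 58 + n₂ for both:

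| Data used | r = 0.5 | r = 0.78 | Narrower by |
|---|---|---|---|
| Experimental arm only, n = 58 | 4.60 | 3.05 | – |
| Both arms, n₂ = 58 | 3.22 | 2.13 | 30% |
| Both arms, n₂ = 46 | 3.40 | 2.26 | 26% |
| Both arms, n₂ = 40 | 3.51 | 2.33 | 24% |
| Both arms, n₂ = 30 | 3.71 | 2.46 | 19% |

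If the arms are weighted equally, the gain is 22% with 40 controls and 15% with 30. The percentages do not depend on the SD.

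**The case against.** The best defence is that the authors meant replication. The sentence goes on to align the arms on the treatment clock, and the design section says the design "provided the opportunity to evaluate the intervention effects in two independent groups at three time points". The Statistical Analysis Plan attaches no test, model or decision rule to the T2/T3 comparison, so the 5% figure assumes an unadjusted two-sample t-test that the plan does not name. Efficacy is tested at T1, and that test is sound.

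The replication purpose is legitimate, and this point does not touch the T1 test. But replication is judged from each arm's change from its own pre-treatment score. Comparing the arms with each other at follow-up shows only whether they end alike, and the sentence gives the intervention effect as its purpose. The cancellation is algebra and holds whatever test is used.

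On stability, the defence is largely right. Using the experimental arm alone is valid and avoids assuming equal maintenance after immediate and delayed treatment. Objective 3 itself names no arm; the restriction lies in the analysis given for it. Control T3 is not discarded, since visit means are reported and the mixed model uses all available data, but neither names a T2–T3 stability contrast. All the half-widths for the mean change are well below 13 points, so no change of conclusion has been shown. This part is a gain in precision, not the correction of an error.

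**Conclusion.** The concern holds. The experimental-T2 versus control-T3 comparison cannot do what Questionnaire Administration says it is for. Its expected value does not depend on the size of a common ICBT effect, and a 13-point effect leaves its rejection rate at 5%, against 98% power at T1 (88% at SD 22). The cancellation rests only on equal effects in the two arms. The percentages also assume 58 evaluable per arm, SD 17.49 unless stated, and no time trend.

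Even as a consistency check the comparison is coarse. Its half-width of 6.4 points is about half the 13-point meaningful change, and it grows with T3 dropout. A non-significant result would not show that the arms are equivalent.

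The omitted control T2–T3 change costs precision only: 15% to 30% of the interval width, depending on how many controls complete T3 and how the arms are weighted. The primary analysis stands. The first part should be corrected before reporting; the second is an inexpensive improvement.

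**What to change.** 1. **Reword the T2/T3 comparison** in Questionnaire Administration as a check of consistency between delayed and immediate treatment, and report the difference with its 95% CI. Alongside it, report each arm's change from its own pre-treatment score (experimental T0–T2, control T1–T3), labelled uncontrolled. Keep T1 as the only between-arm estimate of the ICBT effect.
2. **Extend the stability analysis** in the Statistical Analysis Plan. Keep the experimental T1–T2 change and add the control T2–T3 change, with time recoded to the treatment clock and arm in the model. Show arm-specific estimates and the combined mean change with its 95% CI, and judge stability from that interval.

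The cost is SAP wording and a recoded time variable. Pooling assumes similar maintenance in the two arms, which the data can check only coarsely. The between-arm difference in maintenance has a half-width of 6.4 points (r = 0.5) or 4.3 (r = 0.78) with 58 per arm, and 7.1 or 4.7 with 40 controls. That is why the arm-specific estimates are needed. Neither arm has an untreated comparator in this window, so the stability estimate remains uncontrolled. Parts of the Statistical Analysis Plan describe model fit and a covariate's effect as already known. If results had been seen, the control T2–T3 addition should be labelled post hoc.

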- Participants with a score of 15 or more on the PHQ-9 or indicated self-harm on question 10 will receive a phone consultation from a clinical psychologist on the research team. This call will ensure that they are under care elsewhere or necessary resources and/or referrals can be provided.

Recruitment Strategy

Recruited will involve many strategies including a television broadcast, promoting the study via tinnitus support groups in Texas and the American Tinnitus Association (ATA), and contracting the company "TrialFacts" to boost recruitment. Further recruitment strategies will involve the use of social media (e.g., Facebook and Twitter). Flyers and posters will be distributed to local communities and put up in clinic waiting rooms. Professionals such as audiologists and otolaryngologists in the state of Texas will be notified about the study and provided with leaflets to distribute to suitable patients. Those interested will be directed to the study website (www.tacklingtinnitus.org) where they can read more about the study and register their interest in study participation. Following registration, they will be invited to complete the screening questionnaire. They will be informed of their right to withdraw without penalty at any stage of the process.

Sample Size, Power and Attrition

Sample size estimation will be calculated using G*Power version 3.1.6 (Faul et al., 2007) and based on achieving a 13-point clinically meaning change between baseline and post-intervention using the primary assessment measure, the TFI. Pilot data (Beukes et al., Submitted) indicated 26 participants per group with a 1:1 allocation to achieve 80% power to detect a between-group mean standardized difference effect size of d = 0.50 (a moderate effect size). As this will be fewer than the 58 participants suggested using data from previous RCTs of this intervention, (Beukes et al., 2018) we selected 58 per group. In addition, sample size will be inflated to account for missing data, estimated to be 20% from the US phase I trial data (Beukes et al., 2021b). The aim will be thus to recruit 146 participants with 73 in each arm (calculated as 58/0.8).

Randomization

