Guidance will be provided to support participants while undertaking the intervention. This will include monitoring progress, monitoring weekly scores, providing feedback on worksheets completed, outlining the content of new modules, and answering questions.

Outcome Measures

Primary Outcome Measure

The primary outcome measure will be tinnitus severity as measured by the Tinnitus Functional Index (TFI; Meikle et al., 2012). The TFI has been translated into more than 15 languages and been validated for several populations including Chinese, Dutch, Swedish and German (Henry et al., 2016). It will be selected over other tinnitus questionnaires as it will be specifically developed to measure tinnitus severity and assess responsiveness to treatment and for comparison purposes with previous trials (e.g., Beukes et al., 2018). Meikle et al. (2012) reported that meaningful changes occur when scores are reduced by 13 points or more.

Secondary Outcome Measures

Secondary outcome measures will assess anxiety, depression, insomnia, tinnitus cognitions, hearing-related difficulties, and health-related quality of life, as shown in Table 1. To reduce the assessment load, the Tinnitus and Hearing Survey (THS; Henry, et al., 2015) will be used

to identify hearing disability and hyperacusis as it only includes 10 questions. The section on tinnitus also served as a secondary tinnitus measure. The EQ-5D-5L (Herdman, et al., 2011) will be selected to measure general health-related quality of life. All questionnaires will be used with the required permissions and agreements will be set up for those that are not freely available to use. For Spanish speakers, validated Spanish translated versions will be used. Where these will be unavailable, validated translations will be undertaken (Manchaiah, et al., 2020b).

Weekly Monitoring During the Intervention

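### The follow-up of T1 non-completers describes no TFI-only fallback, although the primary contrast needs only the T1 TFI; offering one at the final call would be a cheap improvement

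*Combined protocol and SAP*

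**What the plan says.** Questionnaire Administration states that the questionnaires are online and that all measures are due at each main time point. Table 1 lists seven instruments at T1: TFI, GAD-7, PHQ-9, ISI, TCQ, EQ-5D-5L with its visual analogue scale, and THS. For people who do not respond, "3 electronic reminders will be sent to participants who had not completed questionnaires, on the 3 consecutive days after the release of the questionnaire". One further reminder goes out by email and text. The last step is a call: "If questionnaires will be still not completed participants will be telephoned to encourage questionnaire completion". No section gives the TFI priority, offers a shortened form, states the order of the questionnaires, or says what happens to a partly completed set.

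The Statistical Analysis Plan defines the endpoint as follows: "The primary study outcome will be a change in TFI score between the groups at postintervention (T1". It plans multiple imputation with a complete-case comparison, and a linear mixed model for each outcome that uses all available data.

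Under Sample Size, Power and Attrition, "sample size will be inflated to account for missing data, estimated to be 20% from the US phase I trial data". The plan is aware of respondent burden: under Secondary Outcome Measures, the 10-item THS was chosen with that aim ("To reduce the assessment load, the Tinnitus and Hearing Survey").

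Under Intervention Variables, direct questioning in the outcome questionnaire is one of three ways in which adverse effects are picked up.

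**The concern.** T1 is the time point that the trial can least afford to lose. It is the only TFI assessment after baseline at which the control group has not yet had ICBT. By T2 the controls have been treated, so a missed T1 TFI cannot be replaced by a later score. The primary contrast needs this one questionnaire out of the seven.

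Some people who decline the full set at the last contact might still complete the TFI alone. If nobody offers that option, their primary outcome has to be imputed. Raising recruitment to 73 per arm restores the number of observed scores, but it does not lower the missing fraction or any bias that comes with it. The Statistical Analysis Plan gives substantial differences as its reason for reporting the imputed results. In context, that means differences between the imputed and complete-case analyses. On the plan's own account, then, missing data matter to the result. Missing TFI scores also bear directly on Cohen's d, which is to be computed from observed data.

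**Working it through.** **Reproducing the plan's figure.** The plan says "we selected 58 per group" and divides by 0.8. 58 / 0.8 = 72.5, rounded up to 73 per arm; 2 × 73 = 146. This agrees with the plan.

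**Inputs from the documents.** Recruited per arm 73; missing data 20% (a general estimate, applied here to the T1 TFI by assumption); two-sided alpha 0.05; d = 0.50 (Sample Size, Power and Attrition); 13 points as a meaningful change; SD 17.49 (given for the reliable change index, not for the sample size).

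**Input not in the documents.** The share f of non-completers who would return a TFI-only form. It is an assumption, shown over its whole range from 0 to 1.

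**Observed T1 TFI scores per arm.** n(f) = 73 × [1 − 0.20 × (1 − f)]. At f = 0, 73 × 0.80 = 58.4; at f = 0.5, 73 × 0.90 = 65.7; at f = 1, 73. Over both arms, 0.20 × 146 = 29.2 scores are missing at f = 0.

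**Power at d = 0.50.** Two-sample t-test, non-centrality d × √(n/2), 2n − 2 degrees of freedom. At f = 0 the non-centrality is 0.50 × √29.2 = 2.70; at f = 1 it is 0.50 × √36.5 = 3.02.

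| Share recovered, f | TFI scores per arm | TFI missing | Power at d = 0.50 | d detectable with 80% power |
|---|---|---|---|---|
| 0 | 58.4 | 20% | 76.4% | 0.523 |
| 0.10 | 59.9 | 18% | 77.4% | 0.516 |
| 0.25 | 62.1 | 15% | 78.9% | 0.507 |
| 0.50 | 65.7 | 10% | 81.2% | 0.492 |
| 1 | 73.0 | 0% | 85.1% | 0.467 |

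With exactly 58 per arm, power is 76.1%.

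**Power for 13 points with SD 17.49.** d = 13 / 17.49 = 0.7433. By the normal approximation, power = Φ(d × √(n/2) − 1.96). At f = 0: 0.7433 × √29.2 = 4.02, so Φ(2.06) = 98.0%. At f = 1: 0.7433 × √36.5 = 4.49, so Φ(2.53) = 99.4%.

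**Can a lone TFI score be used?** Yes. The mixed model is fitted outcome by outcome on all available data, so a T1 TFI without the other six instruments enters the primary analysis unchanged. It also replaces an imputed value in the multiple-imputation analysis.

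**The case against.** Several stronger readings are tempting, and the documents do not support them.

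- *The call accepts only the whole set, and anyone who will not do all of it leaves no primary outcome.* The text says only that completion is encouraged. It does not say that the set is all-or-nothing or that partial responses are discarded. The TFI is the first row of Table 1 and may already be presented first and saved. What can be said is that no fallback is described.
- *The plan expects about 15 of 73 per arm to have no T1 TFI.* The 20% is a general missing-data estimate from the earlier US trial. It is not tied to T1, to the TFI or to complete non-response.
- *The length of the set causes the non-response.* The remark on assessment load explains the choice of the THS, a reduction already made. People still silent after the reminders may have withdrawn or be out of reach, and the recovery could be nil.
- *The trial gains materially in power.* The sample size already allows for 20% loss. The plan attaches d = 0.50 to the pilot-based figure of 26 per group, not to the 58 taken from previous trials. The planned analysis is a mixed model that includes baseline, not a plain t-test. For 13 points with SD 17.49, power is near its ceiling without any recovery.

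A TFI-only form also has a real cost. It would drop the adverse-effect question that sits in the outcome questionnaire, as well as the comorbidity scores needed for the second objective. If it were sent with the email and text reminder, it could divert people whom the call would have brought to full completion.

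All of this stands. It limits the size of the point and shapes the fix. It does not supply the missing fallback.

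**Conclusion.** The point holds as a cheap improvement, not as an error in the plan. The described sequence ends with a call to encourage completion and gives no minimum-data option for the primary outcome, at the one TFI assessment after baseline that precedes treatment of the controls.

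The benefit is fewer missing primary scores and less reliance on imputation, by an amount that the documents do not allow to be estimated. The figures above are an illustration. They rest on three assumptions: that 20% of T1 TFI scores would be missing, that the recovery share lies anywhere between none and all, and that an unadjusted two-sample comparison approximates the planned analysis. On that footing the gain at d = 0.50 is at most about 9 percentage points (76% to 85%) and about 5 points at half recovery. For 13 points with SD 17.49 it is little more than 1 point. The case for the change therefore rests on the missing fraction, not on power.

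**What to change.** In Questionnaire Administration, add to the final telephone contact, and not to the email and text reminder before it, that anyone who will not complete the full T1 set is offered an online link to the TFI plus the adverse-effect question. Keeping it online preserves the same mode of administration in both arms. In the Statistical Analysis Plan, state that these TFI scores enter the planned mixed model and multiple imputation like any other T1 score.

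The cost is one short online form and a line in the script of a call that is already planned. These participants will give no other secondary scores at T1, and a few who would have completed the full set may take the short form. Holding the offer back until the call keeps that second loss small.
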